7.4.3.2.1 Hyperphosphatemia

Dose modifications of rogaratinib for elevated serum phosphate levels ($\geq 7 \text{ mg/dL}$) and management guidance for hyperphosphatemia are presented in Table 7–4.

Table 7–4 Dose modifications of rogaratinib and management for hyperphosphatemia

Serum phosphate	Countermeasures
Initial phosphate value is	Continue rogaratinib at the same dose.
abnormally high, but less than 7 mg/dL	Consider low phosphate diet ^a and / or initiate phosphate chelators.
≥ 7 mg/dL for two weeks despite phosphate lowering treatment	Hold rogaratinib and increase dose of phosphate chelators until recovery below 7 mg/dL.
	Re-start rogaratinib at the same dose level and continue phosphate chelators.
≥ 7 mg/dL despite optimal phosphate lowering treatments and two rogaratinib	Hold rogaratinib and continue phosphate chelators until recovery below 7 mg/dL.
treatment interruptions on the same dose within four weeks	Re-start rogaratinib, but at one dose level lower and continue phosphate chelators.
≥ 7 mg/dL despite optimal phosphate lowering treatments and two rogaratinib	Hold rogaratinib and continue phosphate chelators until recovery below 7 mg/dL.
treatment interruptions within four weeks at 400 mg b.i.d.	Re-start rogaratinib at 400 mg b.i.d. and continue phosphate chelators.

b.i.d. = Twice daily, bis in die.

In case phosphate chelators are not tolerated, low-phosphorus diet should be considered.

For patients with elevated serum phosphate levels ≥ 7 mg/dL, serum phosphate level and standard single 12-lead ECG has to be checked weekly for ≥ 4 weeks until resolution (serum phosphate < 7 mg/dL).

In patients with hypocalcemia of CTCAE Grade ≥ 2 , an additional 12-lead ECG has to be obtained on the day of detection of hypocalcemia and should be repeated as clinically indicated.

b: In case of Grade 2 diarrhea with no signs or symptoms of colitis and that does not resolve within 72 hours with or without supportive care, rogaratinib dosing has to be interrupted until resolution to Grade ≤ 1. No dose reduction is required.

c: If not recovered within 21 days, the study treatment will be permanently discontinued.

d: If dose reductions by more than 2 levels are required, the study treatment will be permanently discontinued.

a: Low phosphate diet can be considered if the patient's nutritional status is not affected.

23 MAY 2023 Version 6.0 Page: 60 of 181

7.4.3.2.2 Liver toxicity

Dose modifications of rogaratinib for liver toxicity are presented in Table 7–5 and have been adapted based on criteria established for liver toxicity due to atezolizumab concomitant administration. Immune-related hepatitis has been associated with the administration of atezolizumab. Refer to the latest available versions of rogaratinib and atezolizumab IBs for further details. Eligible patients must have adequate liver function, as manifested by measurement of hepatic transaminases and total bilirubin, and liver function will be monitored throughout study treatment. Liver toxicity refers to ALT and/or AST and/or bilirubin increases and graded according to CTCAE v.4.03.

23 MAY 2023 Version 6.0 Page: 61 of 181

Table 7–5: Dose modifications of rogaratinib and atezolizumab for liver toxicity

Toxicity	Modification schedule	
Hepatic event, Grade 1	No modifications. Treat as scheduled and check AST, ALT and bilirubin weekly for at least 4 weeks ^a or until values resolve to within normal limits	
Hepatic event, Grade 2	All events:	
with AST or ALT > 3 x ULN and up to 5 x ULN or total bilirubin greater than 1.5 and	No modification. Check AST, ALT and bilirubin level more frequently until return to baseline value	
up to 3 x ULN in absence of an alternative explanation for these elevations	Events of > 5 days' duration:	
ospianation for those dievations	1. STOP rogaratinib	
	2. STOP atezolizumab	
	 Initiate treatment with 1-2 mg/kg/day oral prednisone or equivalent 	
	 Check AST, ALT and bilirubin level weekly or more frequently till recovery to Grade 0-1 a 	
	 After recovery to Grade 0-1 re-start with rogaratinib -1 DL ^b and atezolizumab 	
	 Permanently discontinue atezolizumab and rogaratinib, and contact sponsor if event does not resolve to Grade 0-1 within 12 weeks 	
Hepatic event, Grade 3	Withdraw patient from study treatment permanently a, c, d and	
with AST or ALT > 3 x ULN with concomitant	contact sponsor	
bilirubin > 2 x ULN in absence of an alternative explanation for these elevations	Consider patient referral to gastrointestinal specialist for evaluation and liver biopsy to establish etiology of hepatic injury	
or with AST or AST > 5 x ULN and/or total bilirubin > 3 x ULN in absence of an	Initiate treatment with 1-2 mg/kg/day oral prednisone or equivalent	
alternative explanation for these elevations	If event does not improve within 48 hours after initiating corticosteroids, considering adding an immunosuppressive agent.	
	If event resolves to Grade 1 or better, taper corticosteroids over ≥ 1 months	
Hepatic event, Grade 4	Withdraw patient from study treatment permanently a, c	

ALT = Alanine aminotransferase; AST = Aspartate aminotransferase; DL = Dose level; ULN = Upper limit of normal. a: In case of interruption/discontinuation, check AST, ALT, and bilirubin weekly or more frequently according to local standard of care, until recovery to Grade 0-1 or to baseline.

standard of care, until recovery to Grade 0-1 or to baseline.
b: Dose will not be re-escalated to original dose after dose reduction for toxicity. If more than 2 dose level reductions are required, treatment will be permanently discontinued.

c: Patients with Gilbert's syndrome who develop elevated transaminases should be managed as per the above outlined recommendations for the respective observed elevation of ALT and / or AST.

d: If per investigator' judgment the Grade 3 hepatic event is unrelated to study treatment and reversible, the treatment may be restarted after resolution to Grade 0 or 1 or to baseline.

23 MAY 2023 Version 6.0 Page: 62 of 181

Patients with right upper-quadrant abdominal pain and/or unexplained nausea or vomiting should have liver function tests (LFTs) performed immediately and reviewed before administration of the next dose of study drug.

For patients with elevated liver function tests, concurrent medication, viral hepatitis, and toxic or neoplastic etiologies should be considered and addressed, as appropriate.

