6.4.1.3 Withdrawal criteria

Patients *must* be withdrawn from the study treatment if any of the following occurs:

• Consent withdrawal at their own request or at the request of their legally acceptable

23 MAY 2023 Version 6.0 Page: 48 of 181

representative.

o At any time during the study and without giving reasons, a patient may decline to participate further. The patient will not suffer any disadvantage as a result.

• Substantial non-compliance with study procedures

- Patients requiring a dose interruption of rogaratinib due to toxicity > 21 days from the next intended dose or due to other reasons for > 31 days from the next intended dose will be withdrawn from the study treatment.
- o Off study drug (atezolizumab) longer than 42 days from the next intended dose
 - If, in the judgment of the investigator, the patient is likely to derive clinical benefit from resuming atezolizumab after a hold > 42 days, atezolizumab may be restarted after sponsor approval.
 - If patients must be tapered off steroids used to treat adverse events, atezolizumab may be held for > 42 days. The acceptable length of interruption will depend on agreement between the investigator and the sponsor. (See also Section 7.4.3.3 for further details and specific recommendations).
- Lost to follow-up
- o Use of another non-protocol anti-cancer therapy

• Unacceptable toxicity

- If, in the investigator's opinion, continuation of study would be harmful to the patient's well-being.
- Any toxicity requiring rogaratinib dose reductions below dose level -2.
- Any toxicity requiring rogaratinib dose interruption longer than 21 days to resolve to Grade 1 or better.
- Severe (Grade 3 or higher) allergic reactions such as exfoliative erythroderma, anaphylaxis, or vascular collapse.
- o Severe (Grade 3 or higher) infusion-related reactions.
- Any other potential adverse reaction deemed sufficiently serious to warrant discontinuation of treatment by the investigator or his designated associate(s).

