In the event that a patient experiences a moderate infusion-related event (NCI CTCAE Grade 2) or flushing, fever, or throat pain, the patient should have his or her infusion immediately interrupted and should receive aggressive symptomatic treatment (e.g. oral or i.v. antihistamine, anti-pyretic, glucocorticoids, epinephrine, bronchodilators, oxygen). The infusion should be restarted only after the symptoms have adequately resolved to baseline grade. The infusion rate at restart should be half of the infusion rate that was in progress at the time of the onset of the infusion-related event. For the subsequent infusion, administer oral premedication with antihistamine and anti-pyretic and monitor closely for infusion-related reactions.

For severe or life-threatening infusion-related events (NCI CTCAE Grade 3 or 4), the infusion should be stopped immediately, and aggressive resuscitation and supportive measures should be initiated (administer aggressive symptomatic treatment e.g. oral or i.v. antihistamine, antipyretic, glucocorticoids, epinephrine, bronchodilators, oxygen). Patients experiencing severe or life-threatening infusion-related events will not receive further infusion and will be further managed as clinically indicated until the event resolves.

As per the IB withhold atezolizumab for any of the following:

- Grade 2 pneumonitis
- Aspartate aminotransferase (AST) or alanine aminotransferase (ALT) greater than 3 and up to 5 times upper limit of normal (ULN) or total bilirubin greater than 1.5 and up to 3 times ULN
- Grade 2 or 3 diarrhea or colitis
- Grade 2 or 3 hypophysitis
- Symptomatic adrenal insufficiency,
- Grade 3 or 4 hypothyroidism or hyperthyroidism

23 MAY 2023 Version 6.0 Page: 64 of 181

- Grade 3 or 4 hyperglycemia
- Suspected Stevens-Johnson syndrome (SJS) or toxic epidermal necrolysis (TEN)
- Grade 2 immune-mediated neuropathy, including facial paresis
- Grade 2 ocular inflammatory toxicity
- Grade 2 or 3 pancreatitis, or Grade 3 or 4 increases in amylase or lipase levels (greater than 2.0 times ULN)
- Grade 3 or 4 infection
- Grade 2 infusion-related reactions
- Grade 3 rash
- Grade 1 immune-mediated pericarditis
- Grade 2 immune-related nephritis
- Grade 2 or 3 immune-related myositis

Atezolizumab may be resumed in patients whose adverse reactions recover to Grade 0–1 (except for Grade 1 immune-mediated pericarditis).

Permanently discontinue atezolizumab for any of the following:

- Grade 3 or 4 pneumonitis

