- AST or ALT greater than 5 times ULN or total bilirubin greater than 3 times ULN in the absence of an alternative explanation for these elevations
- Grade 4 diarrhea or colitis
- Grade 4 hypophysitis
- Grade 4 immune-mediated hypothyroidism or hyperthyroidism
- Any grade confirmed SJS or TEN
- Grade 3 or 4 immune-mediated neuropathy, including facial paresis
- Any grade myasthenic syndrome/myasthenia gravis, Guillain-Barré or meningoencephalitis
- Grade 2–4 immune-mediated myelitis
- Grade 3 or 4 ocular inflammatory toxicity
- Grade 4 or any grade of recurrent symptomatic pancreatitis
- Grade 2–4 immune-mediated myocarditis or immune-mediated pericardial disorders
- Grade 3 or 4 immune-related nephritis
- Grade 3 or 4 infusion-related reactions

23 MAY 2023 Version 6.0 Page: 65 of 181

- Grade 4 rash
- Grade 4 immune-related myositis

Management of specific adverse events

Toxicities associated or possibly associated with atezolizumab treatment should be managed according to standard medical practice. Additional tests, such as autoimmune serology or biopsies, should be used to determine a possible immunogenic etiology.

Although most immune-mediated adverse events observed with immunomodulatory agents have been mild and self-limiting, such events should be recognized early and treated promptly to avoid potential major complications. Discontinuation of atezolizumab may not have an immediate therapeutic effect, and there is no available antidote for atezolizumab. In severe cases, immune-mediated toxicities may be acutely managed with topical corticosteroids, systemic corticosteroids, mycophenolate, or TNF- α inhibitors.

The primary approach to Grade 1–2 immune-mediated adverse events is supportive and symptomatic care; for higher grade immune-mediated adverse events, oral or parenteral steroids are given, and either skipping a dose or stopping therapy is appropriate.

If corticosteroids have been initiated, they must be tapered over ≥ 1 month to ≤ 10 mg/day oral prednisone or equivalent before atezolizumab can be resumed.

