	Re-evaluate on serial imaging	Refer patient to pulmonary and infectious disease specialist and consider	Oral or i.v. broad-spectrum
	Consider patient referral to pulmonary specialist	bronchoscopy or BAL with or without transbronchial biopsy	administered in parallel to the immunosuppressive treatment
	For recurrent events, treat as a Grade 3 or 4 event	Initiate treatment with 1–2 mg/kg/day oral prednisone or equivalent	Bronchoscopy or BAL with or without transbronchial biopsy is recommended
		Resume atezolizumab if event resolves to ≤ Grade 1 within 12 weeks	Initiate treatment with 1–2 mg/kg/day i.v. methylprednisone
		Permanently discontinue atezolizumab if event does not resolve to ≤ Grade 1 within 12 weeks and contact the sponsor ^{a, b, c, d}	If event does not improve within 48 hours after initiating corticosteroids, consider adding an immunosuppressive agent
		For recurrent events or events with no improvement after 48–72 hours of corticosteroids, treat as a Grade 3 or 4 event	If event resolves to Grade 1 or better, taper corticosteroids over ≥ 1 month

BAL = bronchoscopic alveolar lavage; CTCAE = Common Terminology Criteria for Adverse Events; i.v. = intravenous.

a: If corticosteroids have been initiated, they must be tapered over ≥ 1 month to ≤ 10 mg/day oral prednisone or equivalent before atezolizumab can be resumed.

b: Atezolizumab may be withheld for a period of time beyond 12 weeks to allow for corticosteroids to be reduced to ≤ 10 mg/day oral prednisone or equivalent. The acceptable length of the extended period of time must be agreed upon by the investigator and the sponsor.

c: Resumption of atezolizumab may be considered in patients who are deriving benefit and have fully recovered from the immune-related event. Patients can be rechallenged with atezolizumab only after approval has been documented by both the investigator (or an appropriate delegate) and the sponsor.

d: In case of pneumonitis, atezolizumab should not be resumed after permanent discontinuation.

23 MAY 2023 Version 6.0 Page: 67 of 181

Immune-mediated hepatitis

Immune-mediated hepatitis, defined as requiring use of corticosteroids and with no clear alternate etiology, occurred in patients receiving atezolizumab treatment. Liver test abnormalities occurred in patients who received atezolizumab. Refer to the latest available version of atezolizumab IB for further details. For management of liver toxicity, refer to the Section 7.4.3.2.2 and Table 7–5.

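### Grade 2 liver events: Table 7-5 conflicts with the atezolizumab withhold list in the first 5 days, and with the 21-day rogaratinib withdrawal rule later on

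*Protocol*

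**What the plan says.** **First days of the event.** Table 7-5 (Protocol 7.4.3.2.2) is titled for rogaratinib and atezolizumab. Its Grade 2 row covers the liver values above when no other cause explains them. For all such events it says: "No modification. Check AST, ALT and bilirubin level more frequently until return to baseline value". Events longer than 5 days stop both drugs and start prednisone.

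Section 7.4.3.3 has a list, attributed to the atezolizumab investigator's brochure (IB), of reasons to withhold atezolizumab. One entry is "Aspartate aminotransferase (AST) or alanine aminotransferase (ALT) greater than 3 and up to 5 times upper limit of normal (ULN", or total bilirubin in the same 1.5 to 3 × ULN band. It sets no minimum duration. Afterwards, "Atezolizumab may be resumed in patients whose adverse reactions recover to Grade" 0–1. Further on, under immune-mediated hepatitis, the same section says: "For management of liver toxicity, refer to the Section 7.4.3.2.2" and Table 7-5.

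**Recovery limit.** For events over 5 days, Table 7-5 restarts rogaratinib at one dose level lower, together with atezolizumab, on recovery to Grade 0–1. The outer limit is: "Permanently discontinue atezolizumab and rogaratinib, and contact sponsor if event does not resolve to Grade 0-1 within 12 weeks". Section 6.4.1.3 lists when patients must be withdrawn from study treatment, and one item is "Any toxicity requiring rogaratinib dose interruption longer than 21 days to resolve to Grade 1 or better". A second item there and a bullet in 7.4.3.2 set the same limit for rogaratinib interruptions due to toxicity. The protocol's definitions make study treatment both drugs.

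**The concern.** These are bedside safety instructions. Section 9.6 requires laboratory values to be reviewed before each infusion. From Cycle 5 the scheduled safety laboratory tests fall on Day 1, the infusion day, and may be drawn up to 2 days before dosing. A new elevation found at a scheduled visit therefore surfaces when the atezolizumab decision is due. If it is unexplained and no more than 5 days old, one text leaves dosing unchanged and another withholds.

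For a longer event, a patient who recovers after day 21 of the rogaratinib interruption may resume under Table 7-5 but must come off both drugs under 6.4.1.3. What is at stake is whether a recovered patient keeps a treatment that may be helping, and whether a site that follows the table commits a protocol deviation.

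**Working it through.** The plan gives no figure to reproduce. The check compares texts, with some day arithmetic.

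**Conflict 1: infusion due in the first 5 days**

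1. Values: the Table 7-5 Grade 2 row and the withhold entry use the same AST/ALT and bilirubin bands.
2. Duration: Table 7-5 acts on dosing only after 5 days. The withhold entry has no duration condition.
3. Meaning of no modification: 7.4.3.3 allows no atezolizumab dose reduction, so leaving it unmodified can only mean giving it.
4. Cause: the Table 7-5 row requires that no other cause explains the values; the withhold entry does not. The matching permanent-discontinuation entry does carry that condition: "AST or ALT greater than 5 times ULN or total bilirubin greater than 3 times ULN in the absence of an alternative explanation". Section 7.4.3.2.2 also asks for a work-up: "concurrent medication, viral hepatitis, and toxic or neoplastic etiologies should be considered and addressed". While that work-up is open, or if another cause is found, the Table 7-5 row may not apply and the withhold entry stands alone.
5. Result: the texts contradict each other only when three things coincide: an event of 5 days or less, an infusion due, and other causes already excluded.

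**Conflict 2: recovery limit**

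1. Table 7-5 limit: 12 weeks × 7 = 84 days. Rogaratinib limit in 6.4.1.3 and 7.4.3.2: 21 days.
2. Start of the 12 weeks: Table 7-5 does not say. Where sibling tables state a start (Table 7-8 hypophysitis, Table 7-9 neuropathy, Table 7-12 renal, Table 7-13 myositis), it is event onset.
3. Clock from onset, rogaratinib stopped after day 5: 84 − 5 = 79 possible days of interruption, and 79 − 21 = 58 days in conflict (interruption days 22–79, event days 27–84). A later stop gives fewer.
4. Clock from the stop of rogaratinib: 84 − 21 = 63 days (interruption days 22–84). Nothing in the text supports this start.
5. Hepatic exception: there is none. In 7.4.3.2, the bullet directly above the 21-day bullet does exempt liver toxicity, but from dose re-escalation only. In 6.4.1.3, the 42-day atezolizumab limit has written exceptions and the 21-day rogaratinib limit just above it has none.
6. The 12-week item in 6.4.1.3 for atezolizumab-related toxicity does not help. Any single item triggers withdrawal, and the 21-day item is reached first.

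**The case against.** The strongest defence is that the protocol already shows which text prevails. For conflict 1, 7.4.3.3 itself sends liver toxicity to Table 7-5, which was adapted to atezolizumab criteria. For conflict 2, 7.4.4 calls 6.4.1.3 the full list of withdrawal criteria, so the table could be read as setting doses and 6.4.1.3 as setting withdrawal.

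Neither pointer removes the contradiction. The first is a cross-reference that leaves the withhold entry standing in the same section. Section 7.2.2 also makes the IB the reference for atezolizumab apart from preparation, and the withhold list is attributed to the IB. The second confirms that 6.4.1.3 is binding, but Table 7-5 still carries its own 12-week discontinuation line.

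Much of the defence does limit the point:

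- A reader might infer that any Grade 2 elevation before an infusion brings contradictory orders. It does not: with laboratory tests at most 2 days old, the work-up will often be open, and then the entry to follow is to withhold.
- A reader might infer that a site can follow either recovery rule and stay within the protocol. For conflict 2 that is wrong: 6.4.1.3 is mandatory, so restarting after day 21 breaches it.
- A reader might count every mention of 21 days as a withdrawal rule. The paragraph in 7.4.3.2 on toxicity after Cycle 1 is permissive, and the Cycle 1 text concerns dose-limiting toxicities. The rules that bind here are the two items in 6.4.1.3 and the matching bullet in 7.4.3.2.
- Conflict 2 needs liver values to stay above Grade 1 for more than 21 days with both drugs stopped and steroids started.
- The population may be small. The Amendment 3 rationale describes patients then remaining as treated for at least 2 years.

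**Conclusion.** Both conflicts are in the current Version 6.0 text, at identical liver thresholds. Conflict 1 is real but narrow, limited to the three coinciding conditions above. Conflict 2 is clearer: a site that follows Table 7-5 after day 21 breaches 6.4.1.3, over at most about 58 days of interruption if the 12 weeks run from onset and rogaratinib stops after day 5.

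A reader might infer that results are at risk. They are not: 5.2.3 plans no further analysis after primary completion. Nor do the documents show that either rule is medically wrong, since the IBs are not among them. Event frequency and the number of patients still on treatment are not given, so no rate is claimed. The point is minor to should-fix: limited in reach, but a contradiction in patient-safety instructions that is cheap to remove.

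**What to change.** 1. Change the first Grade 2 row of Table 7-5 so that a due atezolizumab infusion is withheld until Grade 0–1, with rogaratinib unchanged. This matches the withhold and resume text in 7.4.3.3; the sponsor should confirm it against the current IB.
2. State in 7.4.3.2.2 and 7.4.3.3 which text governs dosing for AST, ALT and bilirubin elevations.
3. Align the recovery limit. The choice is clinical and the sponsor's: either (a) write an explicit Grade 2 hepatic exception to the 21-day rule into both items of 6.4.1.3 and into 7.4.3.2, or (b) put a 21-day rogaratinib limit into Table 7-5 and say whether atezolizumab may then continue alone. Option (b) needs that statement because 7.4.3.3 permits rogaratinib alone during a steroid taper, and I found no text permitting the reverse.
4. Under either option, state whether the recovery clock starts at event onset or at the first held dose.

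The cost is a few lines in a protocol amendment. Amendment 5, which also revised atezolizumab management guidance, was classed as substantial, so these lines are best added to any further amendment; the documents announce none. The clinical downside is an occasional delayed infusion. The SAP does not change.

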Immune-mediated colitis or diarrhea

Immune-mediated colitis or diarrhea, defined as requiring use of corticosteroids and with no clear alternate etiology, occurred in patients receiving atezolizumab. Refer to the latest available version of atezolizumab IB for further details. It is recommended to monitor patients for signs and symptoms of diarrhea or colitis.

All events of diarrhea or colitis should be thoroughly evaluated for other more common etiologies including rogaratinib-related gastrointestinal toxicities. For events of significant duration or magnitude or associated with signs of systemic inflammation or acute-phase reactants (e.g., increased CRP, platelet count, or bandemia): perform sigmoidoscopy (or colonoscopy, if appropriate) with colonic biopsy, with three to five specimens for standard paraffin block to check for inflammation and lymphocytic infiltrates to confirm colitis diagnosis.

Management of immune-related colitis will be according to its severity (Table 7–7).

23 MAY 2023 Version 6.0 Page: 68 of 181

Table 7–7: Management guidelines for immune-mediated gastrointestinal events (diarrhea or colitis)

Event	CTCAE Grade 1	CTCAE Grade 2	CTCAE Grade 3 or 4
Diarrhea or colitis	Continue atezolizumab.	Withhold atezolizumab	Grade 3 Withhold atezolizumab
	Initiate symptomatic	Initiate symptomatic treatment.	
	treatment (oral fluids,	If etrang clinical suspicion for	Refer patients to gastrointestinal
	loperamide, avoid high fiber/lactose diet).	If strong clinical suspicion for immune-mediated colitis, start empiric i.v. steroids while	specialist for evaluation and confirmatory biopsy.
	Endoscopy is recommended if	waiting for definitive diagnosis.	Initiate treatment with 1-2 mg/kg/day intravenous
	symptoms persist for >7 days.	Patient referral to gastrointestinal specialist is recommended.	methylprednisolone or equivalent and convert to 1-2 mg/kg/day oral prednisone or equivalent
	Monitor closely.	recommended.	upon improvement. If event does
		For recurrent event or for events that persist >5 days, initiate treatment with 1-2 mg/kg/day oral prednisone or equivalent. If the event does	not improve within 48 hours after initiating corticosteroids, consider adding an immunosuppressive agent.
		not improve within 48 hours after initiating corticosteroids, consider adding an immunosuppressive agent.	Resume atezolizumab if event resolves to ≤ Grade 1 within 12 weeks. ^{a,b}

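### Table 7-5 and the withhold list in Section 7.4.3.3 give opposite atezolizumab instructions for an unexplained Grade 2 liver event not known to have lasted more than 5 days

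*Protocol*

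**What the plan says.** Protocol Section 7.4.3.2.2 contains Table 7-5, titled "Dose modifications of rogaratinib and atezolizumab for liver toxicity". Its Grade 2 row covers AST or ALT above 3 and up to 5 × ULN, or total bilirubin above 1.5 and up to 3 × ULN, where nothing else explains the rise. For all such events the instruction is "No modification. Check AST, ALT and bilirubin level more frequently until return to baseline value". A second limb, headed "Events of > 5 days" in duration, stops both rogaratinib and atezolizumab, starts prednisone, and allows a restart after recovery to Grade 0–1.

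Section 7.4.3.3 has a separate list introduced by "As per the IB withhold atezolizumab for any of the following". One item gives the same AST/ALT and bilirubin ranges, with no duration condition. After the list the text adds "Atezolizumab may be resumed in patients whose adverse reactions recover to Grade" 0–1.

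Later in Section 7.4.3.3, the paragraph on immune-mediated hepatitis says "For management of liver toxicity, refer to the Section 7.4.3.2.2" and to Table 7-5. It does not say whether the table replaces the liver item in the list.

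**The concern.** A site that sees a Grade 2 liver value before an infusion has two protocol instructions that cannot both be followed. One leaves atezolizumab unchanged while the event is not known to have lasted more than 5 days; the other holds it at once. The list is attributed to the Investigator's Brochure, which Section 7.2.2 makes the reference for atezolizumab in everything except preparation. The table is the organ-specific schedule. A site could reasonably follow either, and would then depart from the other.

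At stake is whether a 1200 mg infusion is given to a patient with unexplained Grade 2 liver values on a drug for which immune-related hepatitis is a stated risk. The point does not extend to rogaratinib dosing, DLT counting or any endpoint.

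**Working it through.** There is no planned figure to reproduce. The check compares the two rules and then asks when they would give different actions.

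**The rules side by side (unexplained event)**

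| | Table 7-5, Grade 2 row | Section 7.4.3.3 list |
|---|---|---|
| AST/ALT | above 3, up to 5 × ULN | above 3, up to 5 × ULN |
| Total bilirubin | above 1.5, up to 3 × ULN | above 1.5, up to 3 × ULN |
| Duration condition | more than 5 days before stopping | none |
| Atezolizumab, 5 days or less, or duration unknown | unchanged | withheld |
| Atezolizumab, more than 5 days | stopped until Grade 0–1 | withheld until Grade 0–1 |

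Section 7.4.3.3 allows no dose reduction of atezolizumab, so the only possible modification is to hold or stop it. An instruction not to modify therefore means not to withhold. The Grade 2 row does not repeat the Grade 1 row's explicit direction to treat on schedule, but for atezolizumab the effect is the same.

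**When the rules diverge**

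Atezolizumab is given on Day 1 of each 21-day cycle (Section 7.4.1.2), and Section 9.6 requires laboratory review before every infusion. The two texts therefore differ in effect only if Grade 2 values are present at an infusion visit and are not known to have lasted more than 5 days.

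Scheduled on-treatment liver tests after the first dose (Table 9-2; Section 9.2.2):

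- Cycle 1: Days 8 and 15, so 0 of 2 fall at an infusion visit.
- Cycles 2–4: Days 1, 8 and 15, so 3 × 3 = 9 tests, of which 3 fall at an infusion visit.
- Cycle 5 onward: Day 1 only, so every scheduled test falls at an infusion visit. The sample may be drawn up to 2 days before dosing.

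Cycle 5 begins on day 4 × 21 + 1 = 85. From then on, Day 1 visits are 21 days apart, or 21 ± 4 = 17 to 25 days with the ±2-day visit windows. Drawing the sample up to 2 days early widens the interval between tests to 15 to 27 days. All of these exceed 5 days. Even the weekly checks that Table 7-5 asks for in a Grade 1 event leave a 7-day gap. When a Grade 2 value is first found at such a visit its onset is unknown, and the site cannot tell whether the 5-day limb applies.

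**Relevance to Version 6.0**

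The rationale for Amendment 3 (Section 15.3) states that patients then on study had been treated for at least 2 years. Two years is 730.5 / 21 = 34.8, or 34 full cycles, well past Cycle 5. Any of those patients still receiving atezolizumab are on the Day-1-only schedule.

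**How the other organ tables treat listed events**

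For pneumonitis, diarrhea or colitis, hypophysitis, neuropathy, pancreatitis, nephritis and myositis, the management table withholds atezolizumab at Grade 2, in agreement with the list. Table 7-7 also uses a 5-day limit, but only for steroids: "For recurrent event or for events that persist >5 days, initiate treatment with 1-2 mg/kg/day oral prednisone or equivalent". Withholding there is immediate. The liver row is the exception.

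**The case against.** The strongest reply is that the protocol largely settles this itself. Section 7.4.3.3 sends the reader to Table 7-5 for liver toxicity and has no separate hepatitis table. The list is a one-line summary by organ, while the table is specific and was adapted for concomitant atezolizumab. On an ordinary reading the specific text governs. This is real mitigation. But the list stands in the same section as an unconditional instruction attributed to the Investigator's Brochure, and nothing qualifies it.

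A second reply is that observing a laboratory-only Grade 2 value fits the protocol's general preference for supportive care at Grades 1–2. Table 7-10 continues atezolizumab for amylase or lipase at 1.5–2.0 × ULN, and Table 7-8 only suggests considering a hold for Grade 2 hypothyroidism. Neither of those is on the withhold list, so neither produces a conflict. What stands is that a short observation period may be clinically acceptable. The documents do not show which rule is right.

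Third, the consequence is narrow. Both rules hold atezolizumab beyond 5 days, closer liver monitoring is already required, and a site that withholds is well inside the 42-day limit. The counts of test days show where the conflict can arise, not how often it does, and the Amendment 3 rationale does not show that anyone still receives atezolizumab. All of this stands and limits the weight of the point; it does not remove the contradiction.

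**Conclusion.** The concern holds. At identical thresholds the current protocol tells sites both to leave atezolizumab unchanged and to withhold it when an unexplained Grade 2 liver event is not known to have lasted more than 5 days, and it states no precedence.

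The size is one infusion decision at a time: 1200 mg given, or held until Grade 0–1. If it is held at once and the event truly lasts 5 days or less, the infusion is delayed by at most 5 days plus the time to retest; a longer event is stopped under both rules. How many patients this touches cannot be estimated.

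The conclusion rests on reading the hepatitis cross-reference as a pointer rather than an override. Its current relevance assumes that at least one patient still receives atezolizumab. This is an internal inconsistency in safety wording: minor, but worth correcting because one of the two instructions must be wrong as written.

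**What to change.** Make both places state the same rule. The choice belongs to the sponsor's clinicians.

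- **Cautious option.** In the Grade 2 row of Table 7-5, withhold atezolizumab while Grade 2 values are present on an infusion day, until Grade 0–1. Keep the 5-day condition for stopping rogaratinib and starting steroids, as Table 7-7 does for steroids.
- **Alternative.** Add the 5-day condition to the AST/ALT/bilirubin item in the Section 7.4.3.3 list, and state that the 5 days run from the first Grade 2 sample, since true onset is unknown when the previous test was about 21 days earlier. A bare reference to Table 7-5 in that item would settle precedence but leave the counting question open.

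Either is a wording amendment to one table row or one list item, with no new scheduled visits; Table 7-5 already asks for more frequent liver tests in a Grade 2 event. The cautious option may delay an occasional infusion by a few days.
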